- h. Because the definition of ACH-related events differed between sites, capture of ACH-related events has been changed to capture all procedures listed in the Schedule of Events to ensure all procedures are collected and analyzed. Tables 9.1.1 and 9.1.2; Section 9.11.6.2; Sections 12.1.2-12.1.11; Sections 12.2.2-12.2.3.

- i. Vital signs instructions now include sitting or supine positions to account for subjects who are too young to sit. The duration of vital signs assessments in Section 9.11.6.5 and Table 9.11.6.5.1 has been extended to align with the assessments presented in the SOE. Additionally, if a dose adjustment visit coincides with a visit at which a full PK is drawn, vital signs will be obtained for 8 hours, similar to the Day 1,2 schedule. Table 9.1.1, *Vital Sign Assessment Frequency* table; Section 9.11.6.5, *Vital Signs*; Table 9.11.6.5.1.
- j. In the event that a sentinel subject has an interrupted dose of study drug on Day 1, instructions have been included for a change in the PK collection schedule. Table 9.1.1 footnote L; Section 9.11.5, *Pharmacokinetics Variables*.
- k. Footnote m in Table 9.1.1 has been updated to correspond to the information in Section 9.11.6.10, *Anti-BMN 111 Immunogenicity Assessments and IgE Testing*.
- l. In Table 9.1.1, footnotes n and o, and Section 9.11.3, *Secondary Efficacy Variables*, text has been added to specify the biomarkers used to assess changes in bone and collagen metabolism.
- m. In Table 9.1.1, footnote q, instruction has been included that efforts to obtain a satisfactory MRI image can be discontinued after 3 unsuccessful attempts.
- n. In Table 9.1.1, footnote v now includes instructions for managing a dose interruption.
- o. Section 9.1.1, *Dose Adjustments*, has been corrected to state that a DMC review will occur after the third sentinel subject reaches Week 12 post-dose adjustment.
- p. In Section 9.3.8, *Duration of Subject Participation*, final follow-up visit for subjects who discontinue from the study has been changed from 2 weeks to 4 weeks after last dose to be consistent with the safety follow-up at 4 weeks in the Schedule of Events.
- q. In Section 9.4.1, *Treatments Administered*, text has been added to reiterate that sentinel subjects will be treated with BMN 111, versus randomized subjects who will receive either BMN 111 or placebo. Additionally, the BMN 111 dose level is subject to potential per-protocol adjustment.

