Dose Adjustments Analysis of available PK data from studies 111-101 and 111-202 indicated that differences in subject body weight did not directly translate to differences in total body clearance of BMN 111. The same weight-based dose in the pediatric population of Study 111-202 (5-12 years old) yielded lower exposure (C_{max} and AUC) than that characterized in the adult population of Study 111-101. Therefore, the same weight-based dose in the young pediatric population in this study may yield exposure less than the target exposure range characterized to be safe and effective in Study 111-202 at the 15- μ g/kg dose. Since this is the first experience with BMN 111 in this young pediatric population, it is also possible the exposure at 15 μ g/kg could be greater than the target exposure range, and dose adjustment may be warranted. Thus, an option for adjustment of the weight-based dose is provided to ensure that the appropriate target exposure for safety and efficacy is reached for the young subjects in this study. The need for dose adjustment will be evaluated as follows: three sentinel subjects in Cohort 1 will receive an initial dose of 15 μ g/kg. After all three sentinel subjects reach Day 8, a review will occur to evaluate all available safety and PK data (at minimum). If the criteria for dose adjustment are met, the three sentinel subjects will be started on the new adjusted dose at their next scheduled visit, and vital signs will be obtained for at least 4 hours post-dose. The remainder of the subjects in the age cohort will also be enrolled starting at the new adjusted dose. After the third sentinel subject reaches Week 12 post-dose adjustment, a DMC review will occur to evaluate all safety and PK data and, upon endorsement, the three sentinel subjects from the next younger cohort will be enrolled starting at the new adjusted dose. The three sentinel subjects for the second and third cohorts will be evaluated similarly to the sentinel subjects in the first cohort for potential dose adjustment. As subjects age on study, they will be administered the dose determined to be appropriate for their current age. For example, if a subject enrolls into Cohort 2 at age 20 months, they will receive the recommended dose for subjects aged \geq 6 to < 24 months until they turn 24 months in age. When they turn 24 months in age, they will begin to receive the recommended dose for subjects aged \geq 24 to < 60 months.		

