NAME OF COMPANY BioMarin Pharmaceutical Inc. [name]	SUMMARY TABLE Referring to Part of the Dossier: Volume: Page:	FOR NATIONAL AUTHORITY USE ONLY:
NAME OF FINISHED PRODUCT: BMN 111		
NAME OF ACTIVE INGREDIENT: Modified rhCNP	Reference:	

STATISTICAL METHODS:

Sample Size Determination: Approximately 70 subjects age 0 to < 60 months at study entry will participate in this study. No formal sample size calculations were performed. The number of subjects is considered appropriate to evaluate the safety and efficacy of BMN 111 in the target population.

Safety Analysis: All subjects who receive at least one dose of study treatment or who are randomized to the placebo-control group in this study will be included in the safety analysis. The safety analysis will be descriptive.

All AEs will be coded using the most current version of Medical Dictionary for Regulatory Activities (MedDRA) to assign system organ class and preferred term classification to event and disease, based on the original terms entered on the eCRF. The incidence of AEs will be summarized by system organ class, preferred term, relationship to study treatment as assessed by the investigator, seriousness, and severity. All AEs, including SAEs and AEs that lead to permanent discontinuation from the study and from the study treatment, will be listed.

All other safety measures including laboratory tests, vital signs, ECG, echocardiogram, hip clinical assessment, and concomitant medication data will also be summarized descriptively. Data summaries will be presented by treatment group (when applicable) for each cohort and overall. All safety results will be listed.

Efficacy Analysis:

All randomized subjects who receive at least one dose of study treatment or placebo in the study will be included in the efficacy analysis.

Efficacy variables, including AGV (based on length/height) and length/height Z-score according to normal reference standards (not ACH), along with their change from baseline will be summarized by treatment group and cohort. Comparisons between treatment groups by cohort on these variables will be carried out where appropriate. Statistical comparisons will be considered descriptive. 95% CIs will be provided along with p values for treatment group comparisons.

Sentinel subjects will be summarized apart for both efficacy and safety.

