Sentinel subjects from each cohort will be enrolled and studied for short-term safety and PK data, after which subjects in all 3 cohorts will be randomized to receive BMN 111 or placebo SC daily (1:1 ratio) for up to 52 weeks. No two sentinel subjects will be dosed on the same day for any cohort. At the start of the study, 3 sentinel subjects will be enrolled and monitored in Cohort 1. After all 3 sentinel subjects reach Day 8, the Sponsor will review and evaluate all available safety data and Day 1 PK data. Based on PK data and criteria set in the protocol, the dose may be adjusted for the sentinel subjects and the rest of the cohort, and will be the starting dose for the younger cohort sentinel subjects. Upon review of the clinical and PK data, the remainder of Cohort 1 (≥ 27 additional subjects) will be enrolled and randomized to treatment with BMN 111 or placebo (1:1 ratio). After the sentinel subjects complete 12 weeks of dosing, a DMC review will occur to evaluate all available safety and PK data. Upon approval by the DMC, the next younger cohort (Cohort 2) will be opened and the 3 sentinel subjects will be enrolled.

The same procedure will be followed for Cohort 2. After all 3 sentinel subjects reach Day 8, the Sponsor will review and evaluate all available safety data and Day 1 PK data. Based on PK data and criteria set in the protocol, the dose may be adjusted for the sentinel subjects and the rest of the cohort, and will be the starting dose for the younger cohort sentinel subjects. Upon review of the clinical and PK data, the remainder of Cohort 2 (≥ 17 additional subjects) will be enrolled and randomized to treatment with BMN 111 or placebo (1:1 ratio). After the sentinel subjects complete 12 weeks of dosing, a DMC review will occur to evaluate all available safety and PK data. Upon approval by the DMC, the youngest cohort (Cohort 3) will be opened and the 3 sentinel subjects will be enrolled.

The same procedure will be followed for Cohort 3. After all 3 sentinel subjects reach Day 8, the Sponsor will review and evaluate all available safety data and Day 1 PK data. Based on PK data and criteria set in the protocol, the dose may be adjusted for the sentinel subjects and the rest of the cohort, and will be the starting dose for the younger cohort sentinel subjects. Upon review of the clinical and PK data, the remainder of Cohort 3 (≥ 17 additional subjects) will be enrolled and randomized to treatment with BMN 111 or placebo (1:1 ratio).

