9.1.1 Dose Adjustments

Analysis of available PK data from studies 111-101 and 111-202 indicated that differences in subject body weight did not directly translate to differences in total body clearance of BMN 111. The same weight-based dose in the pediatric population of Study 111-202 (5-12 years old) yielded lower exposure (C_{max} and AUC) than that characterized in the adult population of Study 111-101. Therefore, the same weight-based dose in the young pediatric population in this study may yield exposure less than the target exposure range characterized to be safe and effective in Study 111-202 at the 15- μ g/kg dose. Since this is the first experience with BMN 111 in this young pediatric population, it is also possible the exposure at 15 μ g/kg could be greater than the target exposure range, and dose adjustment may be warranted. Thus, an option for adjustment of the weight-based dose is provided to ensure that the appropriate target exposure for safety and efficacy is reached for the young subjects in this study.

The need for dose adjustment will be evaluated as follows: three sentinel subjects in Cohort 1 will receive an initial dose of 15 μ g/kg. After all three sentinel subjects reach Day 8, the Sponsor will review and evaluate all available safety and PK data (at minimum). If the criteria for dose adjustment are met, the three sentinel subjects will be started on the new adjusted dose at their next scheduled visit, and vital signs will be obtained for at least 4 hours post-dose.

The remainder of the subjects in the age cohort will also be enrolled starting at the new adjusted dose. After the third sentinel subject reaches Week 12 post dose adjustment, a DMC review will occur to evaluate all safety and PK data and, upon endorsement, the three sentinel subjects from the next younger cohort will be enrolled starting at the new adjusted dose. The three sentinel subjects for the second and third cohorts will be evaluated similarly to the sentinel subjects in the first cohort for potential dose adjustment.

As subjects age on study, they will be administered the dose determined to be appropriate for their current age. For example, if a subject enrolls into Cohort 2 at age 20 months, they will receive the recommended dose for subjects aged ≥ 6 to < 24 months until they turn 24 months in age. When they turn 24 months in age, they will begin to receive the recommended dose for subjects aged ≥ 24 to < 60 months.

Criteria for Dose Adjustment

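### After a sentinel dose adjustment, Section 9.1 and Section 9.1.1 start the 12-week clock for the DMC review that gates the next younger cohort at different points, and neither says which governs.

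*Protocol*

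**What the plan says.** All references are to the amended protocol.

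- **Section 9.1, Cohort 1 paragraph.** After the Day 8 review, "the dose may be adjusted for the sentinel subjects and the rest of the cohort", and the resulting dose becomes the starting dose for the next cohort's sentinels. Then: "After the sentinel subjects complete 12 weeks of dosing, a DMC review will occur to evaluate all available safety and PK data". Then: "Upon approval by the DMC, the next younger cohort (Cohort 2) will be opened and the 3 sentinel subjects will be enrolled". The Cohort 2 paragraph sets the same gate for opening Cohort 3.
- **Synopsis, study design and Data Monitoring Committee paragraphs.** Both repeat the gate at 12 weeks of dosing.
- **Section 9.1.1.** If the adjustment criteria are met, "the three sentinel subjects will be started on the new adjusted dose at their next scheduled visit". The DMC review comes "After the third sentinel subject reaches Week 12 post dose adjustment", and the next cohort's sentinels enrol at the adjusted dose once the DMC endorses it.
- **Synopsis, dose adjustment text.** "After the third sentinel subject reaches Week 12 post-dose adjustment, a DMC review will occur to evaluate all safety and PK data".
- **Summary of changes, item o.** Section 9.1.1 "has been corrected to state that a DMC review will occur after the third sentinel subject reaches Week 12 post-dose adjustment". The item cites Section 9.1.1 only.

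**The concern.** The gate ensures that a younger cohort starts only after a set period of follow-up in the sentinels of the older one, reviewed by the DMC. When no adjustment occurs, the two descriptions do not collide. When one does occur, they give different dates for the same review.

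Section 9.1 is not confined to the unadjusted case. Its own paragraph describes the adjustment and then applies the gate, without restarting the count or referring to Section 9.1.1. The amendment aligned the number of weeks at 12 in both places but left the starting points different. By contrast, item e of the same summary, on dosing by current age, cites both Section 9.1 and Section 9.1.1.

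What is at stake is how much safety and PK experience at the dose to be carried forward the DMC has when it decides.

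**Working it through.** The plan gives no figure of its own to reproduce. The check is date arithmetic.

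**Inputs**

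- Gate under Section 9.1: 12 weeks of dosing, so 12 × 7 = 84 days from first dose.
- Gate under Section 9.1.1: 84 days from the start of the adjusted dose.
- Start of the adjusted dose: the next scheduled visit after the Day 8 review (Section 9.1.1). Table 9.1.1 lists Week 3 and then Week 6, each ±7 days.
- Scheduled PK: Day 1, then Weeks 13, 26, 39 and 52 (Table 9.1.1 and synopsis).

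**Assumption.** The adjusted dose starts at Week 3, or at Week 6 if the review and dose calculation miss Week 3. Week n is taken as 7n days after first dose.

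**Formulas.** With *d* the day on which the adjusted dose starts:

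- weeks at the adjusted dose when the Section 9.1 gate is reached = (84 − *d*)/7
- week of total dosing at the Section 9.1.1 gate = (*d* + 84)/7
- shortfall against 12 weeks = *d*/84

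| Start of adjusted dose | *d* | Weeks at adjusted dose, Section 9.1 gate | Total week of dosing, Section 9.1.1 gate | Shortfall |
|---|---|---|---|---|
| Week 3, −7 days | 14 | 10 | 14 | 16.7% |
| Week 3 | 21 | 9 | 15 | 25.0% |
| Week 3, +7 days | 28 | 8 | 16 | 33.3% |
| Week 6, −7 days | 35 | 7 | 17 | 41.7% |
| Week 6 | 42 | 6 | 18 | 50.0% |
| Week 6, +7 days | 49 | 5 | 19 | 58.3% |

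The two gates differ by *d* days. At nominal visits that is 3 or 6 weeks; with the visit windows it is 2 to 7 weeks.

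**PK available at each gate.** The Week 13 draw is nominally on day 13 × 7 = 91, with a window of days 84 to 98. At 84 days of dosing, the only scheduled PK normally in hand is therefore Day 1, taken before any adjustment. A Week 13 draw could be available only at the very start of its window. The Section 9.1.1 gate falls at week 14 at the earliest (day 98), by which time the Week 13 window has closed. The choice of clock therefore normally decides whether the review can include any scheduled PK at the adjusted dose.

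**The case against.** The strongest reply is that Section 9.1 states the general rule and Section 9.1.1 the specific one. Section 9.1.1 is the only section devoted to what follows an adjustment, its rule is repeated in the amended synopsis, and the summary of changes shows that it was deliberately corrected. Opening the next cohort at the adjusted dose on the Section 9.1 clock alone would breach an express sentence of Section 9.1.1. Neither clock opens a cohort by itself, since DMC approval or endorsement is required on both routes. The DMC charter, which is not available here, may settle the timing.

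Much of this stands. The passages can be read together with Section 9.1.1 governing, and that reading is plausible. But nothing limits Section 9.1 to the unadjusted case or points from it to Section 9.1.1. DMC approval does not remove the conflict either, because the conflict is about when the review takes place and what data it sees.

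A reader might infer something stronger: that infants would be dosed after much less experience at a higher dose. The documents do not support that.

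- Section 9.1 does not say that its 12 weeks count all dosing regardless of an adjustment. That is an inference from its silence.
- The cohort after Cohort 1 is Cohort 2, aged 6 to under 24 months. Cohort 3 is affected only at the step from Cohort 2.
- An adjustment may go either way. It can be triggered by mean exposure below the 25th or above the 75th percentile of the reference group in Study 111-202. The 2-fold limit per kg caps increases only.
- At Week 3 the difference is 9 weeks against 12. The 6-week figure requires the review to miss Week 3.

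**Conclusion.** This is a real internal inconsistency in the current text, worth correcting because it concerns an operative safety gate. It is not evidence that a younger cohort would in fact be started early.

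It matters only if a sentinel dose is adjusted, which the protocol expressly provides for. In that case a literal reading of Section 9.1 gives about 9 weeks at the adjusted dose (8 to 10 with the visit window) for a Week 3 start, or about 6 weeks (5 to 7) for a Week 6 start, against 12 weeks under Section 9.1.1. The review would then normally precede the first scheduled PK draw at the adjusted dose.

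These figures rest on the adjusted dose starting at one of the first two scheduled visits after Day 8; a later start would widen the gap. No view is taken on which interval is clinically right.

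**What to change.** Reconcile the Cohort 1 and Cohort 2 paragraphs of Section 9.1, and the study design and DMC paragraphs of the synopsis, with Section 9.1.1 and the synopsis dose adjustment text. State one clock for the DMC gate when the sentinel dose has been adjusted, cross-refer to Section 9.1.1, and use the same clock in the DMC charter. If amended Section 15 carries the same 12-week wording, align it too; its amended text was not available for this check.

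The cost is wording only. Depending on how the passages are reconciled, cohort opening may move by about 3 to 6 weeks in the adjusted-dose case. Nothing changes when no adjustment is made.

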Genomic biomarkers (optional) ^f		X	
Weight		X	X
Body mass index (calculated)		X	X
Clinical outcome assessment: Bayley-III ^g		X	
Clinical outcome assessment: ITQOL ^g		X	
Capture all procedures in the Schedule of Events		X	X
Adverse events ^h	X	X	X

^a Screening and Day 1 (Month 0) assessments may be performed on the same calendar day at the discretion of the investigator. If Screening and Day 1 (Month 0) are done on the same day, vital signs are taken only once. Please refer to eCRF Completion Instructions.

^b A complete physical examination will be performed at Screening. Complete physical exam includes major body systems, including assessment of general appearance; CV; dermatologic; head, eyes, ears, nose, and throat; lymphatic; respiratory; gastrointestinal (GI); musculoskeletal; and neurological/psychological and genitourinary.

^c Vital signs will be measured with appropriate blood pressure cuffs for achondroplasia children following detailed instructions in Study Reference Manual. At screening, blood pressure should be taken with subject in a supine position, after the subject has been resting for at least 5 minutes. At all other visits, blood pressure should be taken one time after at least 5 minutes of rest, with subject in a supine position. Heart rate should be taken at each time point that blood pressure is measured. Left brachial arm should be the first method of assessment considered, and the same site should be used for blood pressure measurement in each subject throughout the study. The method and site of blood pressure measurement will be recorded and should be utilized consistently throughout the remainder of the study.

^d Growth parameters (anthropometric measurements) may include but are not limited to height, standing height, sitting or supine height, weight, upper and lower arm and leg length, and arm span. Body proportion measurements may include but are not limited to upper:lower body segment ratio, upper arm:forearm length ratio, upper leg:lower leg length ratio, and arm span:standing height ratio. Refer to the Anthropometric Measurement Guidelines for specific instructions regarding the collection of growth measurements. All age-appropriate physical measurements will be collected at approximately the same time each visit (± 2 hours) by a trained study staff member; every effort will be made to have the measurements collected by the same study staff member, if possible, throughout the study. Each measurement will be taken in triplicate (excluding weight, taken once).

^e Vitamin D (25-hydroxy) and alkaline phosphatase will be measured during Screening and at the 3-month visit.

^f If sample is not collected at Day 1, it may be drawn at any time during the study. The sample will be used for exploratory genomics including, but not limited to, NPR-B, BRAF, and other genes associated with CNP signaling.

^g Bayley-III is waived for subjects < 1 month old; ITQOL is waived for subjects < 2 months old.

^h AEs will be collected at screening. For subjects enrolled in Cohort 3 (0 to < 6 months old), the collection period for all AEs begins after informed consent is obtained.

9.1.1 Dose Adjustments

Analysis of available PK data from studies 111-101 and 111-202 indicated that differences in subject body weight did not directly translate to differences in total body clearance of BMN 111. The same weight-based dose in the pediatric population of Study 111-202 (5-12 years old) yielded lower exposure (C_{max} and AUC) than that characterized in the adult population of Study 111-101. Therefore, the same weight-based dose in the young pediatric population in this study may yield exposure less than the target exposure range characterized to be safe and effective in Study 111-202 at the 15- μ g/kg dose. Since this is the first experience with BMN 111 in this young pediatric population, it is also possible the exposure at 15 μ g/kg could be greater than the target exposure range, and dose adjustment may be warranted. Thus, an option for adjustment of the weight-based dose is provided to ensure that the appropriate target exposure for safety and efficacy is reached for the young subjects in this study.

The need for dose adjustment will be evaluated as follows: three sentinel subjects in Cohort 1 will receive an initial dose of 15 μ g/kg. After all three sentinel subjects reach Day 8, the Sponsor will review and evaluate all available safety and PK data (at minimum). If the criteria for dose adjustment are met, the three sentinel subjects will be started on the new adjusted dose at their next scheduled visit, and vital signs will be obtained for at least 4 hours post-dose.

The remainder of the subjects in the age cohort will also be enrolled starting at the new adjusted dose. After the third sentinel subject reaches Week 12 post dose adjustment, a DMC review will occur to evaluate all safety and PK data and, upon endorsement, the three sentinel subjects from the next younger cohort will be enrolled starting at the new adjusted dose. The three sentinel subjects for the second and third cohorts will be evaluated similarly to the sentinel subjects in the first cohort for potential dose adjustment.

As subjects age on study, they will be administered the dose determined to be appropriate for their current age. For example, if a subject enrolls into Cohort 2 at age 20 months, they will receive the recommended dose for subjects aged ≥ 6 to < 24 months until they turn 24 months in age. When they turn 24 months in age, they will begin to receive the recommended dose for subjects aged ≥ 24 to < 60 months.

Criteria for Dose Adjustment

The criteria for dose adjustment are based on obtaining equivalent exposure characterized to be safe and effective with the 15- μ g/kg dose in Study 111-202 in each of the age cohorts evaluated in this study. BMN 111 dose may be adjusted if the mean observed AUC_{0-120} from

sentinel subjects is less than the 25th percentile for AUC₀₋₁₂₀ in Cohort 3 (15 µg/kg) of Study 111-202 or greater than the 75th percentile in Cohort 3 of Study 111-202. If these criteria are met, an allometric scaling coefficient, α , for BMN 111 clearance by subject body weight will be determined using a population PK modelling approach and available data from this study and Studies 111-202 and 111-101. The recommended adjusted dose will be determined using the following expression:

$$Dose_{ch} = Dose_{ref} \left(\frac{WT_{ch}}{WT_{ref}} \right)^\alpha$$

where WT_{ref} and $Dose_{ref}$ are the typical (i.e., median) subject body weight and total dose, respectively, at the 15 µg/kg dose level in Cohort 3 of Study 111-202, and WT_{ch} is the anticipated median weight in the age cohort being studied. As such, the recommended adjusted dose will target the median AUC₀₋₁₂₀ observed at the 15 µg/kg dose level of Study 111-202. The recommended adjusted dose, $Dose_{ch}$, will be normalized by WT_{ch} , to provide the recommended adjusted weight-based dose. The following rules will be used for dose adjustment:

- A maximum of a 2-fold increase in dose/kg will be permitted between dose adjustments regardless of exposure.
- The total dose will not exceed the highest total dose administered in Study 111-202.

